11. MEASUREMENT OF EFFECT

Response criteria in this study are the CTCAE toxicity criteria measuring palmo-plantar erythrodysesthesia.

CTCAE	Grade 1	Grade 2	Grade 3
Palmo-plantar Erythrodysthesia	Minimal skin changes (e.g. erythema, edema or hyperkeratosis without pain)	Skin changes (e.g. peeling, blisters, bleeding, fissures, edema, or hyperkeratosis) with pain; limiting instrumental ADLS	Severe skin changes (e.g. peeling, blisters, bleeding, fissures, edema, or hyperkeratosis) with pain; limiting self-care ADLS

11.1 Antitumor Effect – Solid Tumors

N/A; tumor response is not an objective of this study.

12. DATA REPORTING / REGULATORY REQUIREMENTS

Adverse event lists, guidelines, and instructions for AE reporting can be found in Section 7.0 (Adverse Events: List and Reporting Requirements).

12.1 Data Reporting

12.1.1 Method

The clinical research coordinators will collect and manage the data on this study. The Office of Data Quality (ODQ) may audit this study to perform quality checks on the data for this study.

12.1.2 Responsibility for Data Submission

Clinical research coordinators will enter data and surveys into RedCap.

12.2 Data Safety Monitoring

The DF/HCC Data and Safety Monitoring Board (DSMB) will review and monitor study progress, toxicity, safety and other data from this study. The Board is chaired by a medical oncologist from outside of DF/HCC and its membership composed of internal and external institutional representation. Information that raises any questions about participant safety or protocol performance will be addressed by the Overall PI, statistician and study team. Should any major concerns arise, the DSMB will offer recommendations regarding whether or not to suspend the study.

The DSMB will meet twice a year to review accrual, toxicity, response and reporting information. Information

to be provided to the DSMB may include: participant accrual; treatment regimen information; adverse events and serious adverse events reported by category; summary of any deaths on study; audit results; and a summary provided by the study team. Other information (e.g. scans, laboratory values) will be provided upon request.

12.3 Collaborative Agreements Language

N/A. This is not a CTEP/NCI study

13. STATISTICAL CONSIDERATIONS

In this randomized, double-blind, signal-detection trial, patients will be randomly assigned (1:1) to tazarotene gel plus BPS or placebo gel plus BPS.

13.1 Study Design/Endpoints

Endpoints

The primary endpoint will be the proportion of patients in each arm who develop grade-2 or higher HFSR within the first 8 weeks of protocol therapy. A parallel secondary endpoint will be the proportion of patients in each intervention arm who develop HFSR of any grade.

Efficacy Analysis

Primary Endpoint: For each comparison, the proportion of patients with grade-2 or higher HFSR will be compared between placebo gel plus BPS and tazarotene gel plus BPS using a two-group chi-squared test. The difference between the two proportions will be summarized with a 90% confidence interval.

13.2 Sample Size, Accrual Rate and Study Duration

The total maximum sample size will be 70 patients (35 per arm); the minimum sample size will be 28 patients (14 per arm). The sample size for the comparison is based on a superiority design for the difference in proportions and includes one interim look for futility. We expect this study to be open to accrual for 24 months. We anticipate accruing 3 participants/month.

Based on our prior experience with BPS alone, we expect that 40-50% of patients will develop grade-2 or higher HFSR during treatment with regorafenib. The addition of tazarotene to BPS would be worthy of further study if the observed rate of HFSR is reduced to 25%. When the sample size in each arm is 35 patients, a two-group, chi-squared test with a 0.10 one-sided significance level will have 80% power to detect the difference between a proportion of 50% with HFSR using placebo gel plus BPS and 25% with tazarotene plus BPS.

An interim look for futility will be conducted after a total of 28 patients have been treated (14 with tazarotene gel plus BPS and 14 with placebo gel plus BPS; 40% information). Based on a power family beta spending function (parameter=0.3), if the chi-squared p-value at the interim look is greater than or equal to 0.458 (Z-score

> -0.107) then there will be insufficient evidence in favor of the tazarotene arm and enrollment will stop. Under this design, the probability of stopping at the time of the interim look is 0.543 if the true rate of HFSR is 50% (EaST 5.4).

Secondary comparisons will be based on the incidence of all-grade HSFR in patients treated with regorafenib. Our prior experience would suggest that the incidence of all-grade HSFR to be about 55% for patients using placebo gel plus BPS. For sample sizes of 35 patients per arm, a two-group chi-squared test with a 0.10 one-sided significance level would have 82% power when the incidence of HSFR in the intervention arm is 30%. We will also summarize the proportions of patients who develop non-HSFR adverse events that require cessation of study therapy.

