9. BIOMARKER, CORRELATIVE, AND SPECIAL STUDIES

Correlative studies are optional.

Patients will be asked if they would like to participate until 16 patients are identified.

- Day 1 and 4-week (+/- 2 weeks) skin biopsies will be obtained and processed in formalin fixed, paraffin embedded blocks. The pre-biopsy will be obtained from the non-dominant lateral palm. The 4-week biopsy will be obtained from the same area or an area of HFSR, if present.
- A 4mm punch biopsy will be obtained from up to 16 patients (up to 6 will be analyzed in each study arm); we suspect that half of patients in the control arm will develop HFSR on regorafenib and half will not. This will allow for comparison across arms and between affected and non-affected individuals to look for a signal of difference.

Biopsies will be analyzed using standard immunohistochemistry and cyclic immunofluorescence, for the presence of activation of transcription factors known to be associated with hyper-proliferative inflammatory acquired and genetic skin disorders.

Additionally, RNA transcriptional profiling will be performed to compare those patients who develop HFSR from those who do not use the Nanostring platform on formalin-fixed, paraffin embedded tissue. Gene sets previously developed for inflammatory skin disorders will be used.

Skin biopsy specimen collection and shipment will be paid for by Bayer Pharmaceuticals.

Left over specimens will be banked for future use.

The study team will have access to banked specimens.

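### Does quoting 80% power only for a 50% control rate, the top of the expected 40-50%, call for a change?

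*Combined protocol and SAP*

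**What the plan says.** Section 13.1 defines the primary endpoint as the proportion of patients who "develop grade-2 or higher HFSR within the first 8 weeks of protocol therapy". The arms are compared by a two-group chi-squared test, and the difference is summarised with a 90% confidence interval.

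Section 13.2 sets the planning values. For BPS alone, "we expect that 40-50% of patients will develop grade-2 or higher HFSR during treatment with regorafenib". The bar for interest is put this way: "The addition of tazarotene to BPS would be worthy of further study if the observed rate of HFSR is reduced to 25" per cent. Power is then stated for a single pair of rates, "a proportion of 50% with HFSR using placebo gel plus BPS and 25% with tazarotene plus BPS": it is put at 80% for 35 per arm, tested one-sided at 0.10. One futility look is taken at 28 patients (14 per arm). Enrolment stops if the p-value there is 0.458 or more, with the Z-score bound given as -0.107.

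No power is given for a 40% or 45% control rate. The only other power figure in Section 13.2 (82%, 55% against 30%) concerns the all-grade secondary endpoint, for which the control rate is put at about 55%.

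**The concern.** The plan names a range of control rates and one target, then quotes power at the end of the range where the difference is largest. A fall from 50% to 25% is 25 points, and a fall from 40% to 25% is 15. Both start inside the expected range and reach the stated target, but they are very different detection problems for 35 patients per arm.

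Three statements make 50% look more like an upper limit than a central value:

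- The 40-50% is expected over regorafenib treatment, while the endpoint stops at 8 weeks. In the same patients the 8-week rate cannot be higher.
- With all-grade HFSR at about 55%, a 50% rate of grade 2 or higher means 50/55 = 91% of cases reach grade 2. A 40% rate means 40/55 = 73%.
- In describing the biopsy work, Section 9 says "we suspect that half of patients in the control arm will develop HFSR on regorafenib and half will not".

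The stake is how a negative result is read. If the truth were 40% against 25%, about half of such trials would miss the effect and a quarter would stop at 28 patients. A reader who remembered only the 80% might take that as evidence against tazarotene.

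**Working it through.** **Inputs (Sections 13.1 and 13.2).** 35 per arm, one-sided alpha 0.10 (critical value 1.2816), uncorrected chi-squared test, tazarotene rate 0.25, control rate 0.50, 0.45 or 0.40. Look at 14 per arm, then 21 more per arm. Here Z is signed so that positive values favour tazarotene, so the trial continues if Z exceeds 0.107.

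**Step 1: reproduce the plan's figures.** With d the difference and p̄ the mean of the two rates, power = Φ[(d − 1.2816·s0)/s1], where s0 = √(2p̄(1−p̄)/35) and s1 = √(p1(1−p1)/35 + p2(1−p2)/35).

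At 0.50 against 0.25: p̄ = 0.375, s0 = 0.1157, s1 = 0.1118. (0.25 − 0.1483)/0.1118 = 0.910, and Φ(0.910) = 81.8%. Exact binomial enumeration gives 80.9%. The stated 80% is reproduced. The stated stopping probability of 0.543 when the arms do not differ is also reproduced, as Φ(0.107) = 0.543.

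**Step 2: the same formula lower in the range.**

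- 0.45 against 0.25: s0 = 0.1140, s1 = 0.1115. (0.20 − 0.1461)/0.1115 = 0.483, power 68.6%.
- 0.40 against 0.25: s0 = 0.1120, s1 = 0.1105. (0.15 − 0.1435)/0.1105 = 0.059, power 52.3%.

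**Step 3: exact enumeration, with the look.** The plan gives no separate final boundary, so two are shown: 1.2816, and 1.208, which on normal theory spends the full 0.10 if the futility rule is binding.

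| Control rate | No look | Look, final 1.2816 | Look, final 1.208 | Futility stop |
|---|---|---|---|---|
| 50% | 80.9% | 76.4% | 79.7% | 11.3% |
| 45% | 67.8% | 62.9% | 67.3% | 17.5% |
| 40% | 52.2% | 47.6% | 51.7% | 25.5% |

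**Step 4: would the planned report mislead?** Take a near miss at a 40% control rate: 14/35 against 9/35. The pooled Z is 1.272 and one-sided p = 0.102, not significant. The difference is 5/35 = 14.3 points, with standard error √(0.400×0.600/35 + 0.257×0.743/35) = 0.111. The 90% interval is 14.3 ± 1.645×11.1, about −4 to 33 points. For a futility stop with, say, 5/14 in each arm, the standard error is √(2×0.357×0.643/14) = 0.181, and the interval is about −30 to 30 points. Neither could be taken to exclude a worthwhile benefit.

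**Step 5: the 25% sentence as written.** It speaks of an observed rate. An observed 40% against 25% gives 0.15/0.1120 = 1.34, one-sided p = 0.090, which passes. In whole patients, 14/35 against 8/35 gives p = 0.061 and 14/35 against 9/35 gives 0.102. Read that way, 35 per arm roughly fits the stated bar even at the bottom of the range.

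**Step 6: what covering the range would cost.** By exact enumeration, 80% power against 25% needs 52 per arm without a look or 58 with one at a 45% control rate, and 85 or 100 at 40%. That is 104-116 or 170-200 patients. At 3 per month this is 104/3 to 116/3, about 35-39 months, or 170/3 to 200/3, about 57-67 months. The plan allows 24 months, which yields 24×3 = 72.

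**The case for a change.** The strongest case for a change is that the shortfall is not confined to an extreme. Even at the midpoint of the plan's own range, power is 63-68%. The allowance made for a signal-detection trial has already been used on a one-sided 0.10 level. Reading the aim as a halving does not rescue it, since 40% against 20% gives 66.6% with the look and 71.9% without. Section 2.1 cites any-grade rates of 46.6% in metastatic colorectal cancer and 50% in hepatocellular carcinoma, so a 50% rate of grade 2 or higher would match or exceed the any-grade rate in those tumours. The remedy could be text alone.

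The arithmetic stands in full. So does the observation that the plan is silent on power below 50%.

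The argument that 50% is a ceiling is weaker. The remark about half of control patients concerns a small optional biopsy cohort, names no grade and is not an incidence estimate for the endpoint. Section 2.1 also gives 60.2% for GIST, 71.4% for renal cell carcinoma and 40-85% overall, and eligibility is open to solid tumours generally. The treatment-period wording appears in a paragraph that sizes the 8-week endpoint, and no separate 8-week figure exists to compare it with. The control rate is uncertain, and 50% remains a possible value.

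Nor is the feared misreading built into the plan. Its futility wording speaks of insufficient evidence in favour of tazarotene, which does not assert absence of effect.

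**Conclusion.** No change is needed. The stated 80% is right for the pairing to which the plan ties it, and the design comes close to it once the look is counted (76.4-79.7%). Lower power against a smaller difference is a property of any trial sized on one alternative. Here it is about 63-68% at a 45% control rate and 48-52% at 40%, with a 17-25% chance of a futility stop at 28 patients. These figures assume a true tazarotene rate of 25%, an uncorrected chi-squared test, complete 8-week outcomes and one of the two final boundaries shown.

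The gap is a missing sensitivity table, which an analyst can supply from the plan's own inputs. Adding it to Section 13.2 would be a courtesy to readers and would not alter the test, the sample size or the stopping rule. If the control rate comes in below 50% and the result is negative, the planned 90% interval is the right thing to read. Enrolling 104 to 200 patients to cover the lower rates is out of proportion for a signal-detection study whose recruitment, by Section 4.1, depends wholly on referrals. Accepting lower power below 50% is a fair trade-off.

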1.2 Primary Objectives

To test the hypothesis that the preventative use of 0.1% tazarotene gel daily in addition to BPS (20% urea cream daily, with pharmacy call and DFCI approved teaching sheets) reduces the development of grade-2 or greater hand-foot skin reaction (HFSR) compared with placebo gel plus BPS.

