13.5 Analysis of Primary Endpoints

Please see 13.2 Analysis of Secondary Endpoints

Additional secondary endpoints include investigation of whether tazarotene plus BPS improves health-related quality of life associated with HFSR as assessed using Skindex-16 survey, dermatology quality life index (DLQI) and hand-foot syndrome 14-item scale (HFS-14) prior to initiating the TKI, then at 2-4 week intervals depending on the tool.

Secondary endpoints also include investigation of whether the intervention decreases global stress associated with HFSR as measured prior to initiating the TKI, then at 4 week intervals using the 10-item perceived stress scale (PSS), which has been validated in both healthy people and cancer patients.

The DLQI, Skindex-16 and HFSR are validated dermatologic tools that will be administered every 2 weeks and collect findings based on the past week. The PSS is based on the prior month and will be administered every 4 weeks. The PSS is a validated measure of global stress in cancer patients.

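### Does the 25% observed-rate sentence in section 13.2 create a second go criterion that conflicts with the one-sided 0.10 test?

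*Combined protocol and SAP*

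**What the plan says.** Section 13.2 gives the planning inputs in sequence. The control rate comes first: "we expect that 40-50% of patients will develop grade-2 or higher HFSR during treatment with regorafenib". The sentence in question follows: "The addition of tazarotene to BPS would be worthy of further study if the observed rate of HFSR is reduced to 25" per cent. The power statement comes next: with 35 patients per arm, "a two-group, chi-squared test with a 0.10 one-sided significance level will have 80% power" to distinguish "a proportion of 50% with HFSR using placebo gel plus BPS and 25% with tazarotene plus BPS".

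Elsewhere, the primary objective (1.2) is to test the hypothesis that tazarotene "reduces the development of grade-2 or greater hand-foot skin reaction (HFSR) compared with placebo gel plus BPS". Section 13.1 says that the proportions "will be compared between placebo gel plus BPS and tazarotene gel plus BPS using a two-group chi-squared test" and adds a 90% confidence interval for the difference. On the primary endpoint, section 13.5 says only "Please see 13.2". The interim rule in 13.2 is also a comparison of arms: at 14 patients per arm, enrolment stops if the chi-squared p-value is at least 0.458 (Z above -0.107).

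**The concern.** The sentence is the only place where the plan says what would make tazarotene worth pursuing, and the word *observed* ties it to trial data. Taken at face value it is a single-arm cutoff: look at the tazarotene rate and proceed if it is 25% or lower. The 80% power belongs to a different rule, the two-arm test. No sentence says in so many words that the final conclusion rests on that test, and its level appears only in the power statement.

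In a signal-detection trial the decision to go further is the main product. If both criteria were in force, some results would pass one and fail the other, and the choice between them could be made after the data were seen. A literal cutoff would also have much less than 80% chance of success at the design alternative, and it would not protect against a low event rate in both arms.

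**Working it through.** **Inputs (13.2).** 35 per arm; one-sided 0.10 (critical value 1.2816); design rates 50% and 25%; expected control rate 40-50%; futility look at 14 per arm.

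**The plan's own figure.** The pooled SE is sqrt(0.375 × 0.625 × 2/35) = 0.1157. The unpooled SE is sqrt((0.25 + 0.1875)/35) = 0.1118. Power = Φ[(0.25 - 1.2816 × 0.1157)/0.1118] = Φ(0.909) = 0.818. Exact binomial enumeration without the interim look gives 0.809. The stated 80% is reproduced, and it is the power of the test.

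**The literal cutoff in counts.** 25% of 35 is 8.75, so *at most 25%* means at most 8/35 (22.9%). A lenient reading admits 9/35 (25.7%).

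**Where the cutoffs lie.** Let Z = (x_T/n - x_C/n)/sqrt(p̄(1 - p̄) × 2/n), where x_T and x_C are the tazarotene and placebo event counts and p̄ is the pooled rate. The test is positive if Z ≤ -1.2816. The largest tazarotene count that still gives a positive test is:

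| Placebo events of 35 | 12 | 13 | 14 | 15 | 16 | 17 | 18 |
|---|---|---|---|---|---|---|---|
| Largest x_T | 7 | 8 | 8 | 9 | 10 | 11 | 12 |

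The test cutoff equals 8/35 only at 13 or 14 placebo events. Two examples of disagreement:
- 17/35 versus 11/35: p̄ = 28/70 = 0.40, SE = sqrt(0.24 × 2/35) = 0.1171, Z = -0.1714/0.1171 = -1.46, p = 0.072. The test is positive, but the tazarotene rate is 31%.
- 12/35 versus 8/35: p = 0.145. The rate is met, but the test is negative.

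**Probabilities.** Binomial outcomes were enumerated exactly: stop at 14 per arm if Z > -0.107, otherwise continue to 35 per arm. *Rate met* means that the trial is completed with x_T ≤ 8.

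| Placebo / tazarotene | Test positive | Rate met | Positive, rate above 25% | Rate met, test negative | Disagree |
|---|---|---|---|---|---|
| 50% / 25% | 0.764 | 0.454 | 0.317 | 0.007 | 0.324 |
| 45% / 25% | 0.629 | 0.437 | 0.215 | 0.023 | 0.238 |
| 40% / 25% | 0.476 | 0.411 | 0.119 | 0.055 | 0.174 |

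If 9/35 counts, *rate met* becomes 0.591 and *disagree* 0.221 at 50%/25%; at 40%/25% they are 0.525 and 0.171.

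Most of this gap is mechanical. A cutoff placed at the true rate is met about half the time whatever the design: with a true rate of 25%, the chance of at most 8/35 is 0.474, and of at most 9/35 is 0.626, before any interim stopping.

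**False go with equal arms.** If either criterion sufficed, the chance of a go would be 0.083 at 50% and 0.086 at 40%, against 0.083 and 0.082 for the test alone. It rises to 0.170 at 30% and 0.270 at 25% (test alone 0.089 at both), but those equal-arm rates are assumptions below the plan's 40-50% range.

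**Which reading fits the text.** The order in 13.2 is control rate, target rate, power, and the power statement uses the same 25% as the assumed tazarotene proportion. The word *reduced* implies a comparator, and the preceding sentence supplies one. Sections 1.2 and 13.1 and the futility rule are all between-arm comparisons. Sections 13.1, 13.5 and 13.6.2 contain no threshold on the observed tazarotene rate.

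**The case for a change.** The best argument for a change is that the text does say *observed*, that nothing else in the plan defines a positive final result, and that the interim look has an explicit action rule while the final analysis has none. A result such as 17/35 versus 11/35 is quite possible under the design assumptions. It would satisfy the test and fail the sentence. On this argument either reading calls for an edit: if a target was meant the word is wrong, and if a threshold was meant its operating characteristics are missing. The edit would cost two sentences.

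The facts in this argument stand. The word is inexact, and the final rule has to be assembled from 13.1 and 13.2. The argument does not show that a competent analyst would be left in doubt. The test, its direction and its level are all given, and the objective is framed as a hypothesis test against placebo. At 50% versus 25%, almost all the disagreement (0.317 of 0.324) consists of trials with a positive test and an observed rate above 25%. There the primary objective is met, and the test result would be reported in any case with the difference and its 90% interval.

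**Conclusion.** No change is needed. The sentence is a loosely worded planning target, and the working rule is the two-group chi-squared test at one-sided 0.10. A literal observed-rate rule would be met in 45% of trials at 50% versus 25% (59% if 9/35 is accepted), against 76% for the test, all with the futility look. These figures describe a rule that no analysis section adopts. The stated 80% power is unaffected. Within the plan's 40-50% range, even treating the sentence as an alternative route to a go would barely raise the false-go rate (0.086 against 0.082 at 40%, no difference at 50%).

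This conclusion assumes that 25% means the true tazarotene rate, as the power statement uses it, and that the analysts follow 13.1 and 13.2. Writing *true* for *observed* would be a harmless editorial correction, but it would alter no sample size, error rate, analysis or result.

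### The 82% power for the all-grade comparison is fixed-sample power that leaves out the futility look; with the look it is about 75-77% at the design rates

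*Combined protocol and SAP*

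**What the plan says.** All the relevant statements are in the combined protocol and SAP, section 13.2, apart from the allocation ratio (section 13) and the status of the endpoint (section 13.1).

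- Size and allocation: "The total maximum sample size will be 70 patients (35 per arm); the minimum sample size will be 28 patients (14 per arm"); "patients will be randomly assigned (1:1) to tazarotene gel plus BPS or placebo gel plus BPS".
- Primary power: 80% for grade-2-or-higher rates of 50% v 25%, 35 per arm, chi-squared, one-sided 0.10. The expected control rate is given as 40-50%. The sample size is said to include the futility look.
- Futility look: "An interim look for futility will be conducted after a total of 28 patients have been treated", 14 per arm. Then, "if the chi-squared p-value at the interim look is greater than or equal to 0.458" (Z above -0.107), there is "insufficient evidence in favor of the tazarotene arm and enrollment will stop".
- All-grade power: from earlier experience the plan expects an all-grade rate of about 55% on placebo gel. It takes 35 per arm and the same chi-squared test at one-sided 0.10, and states that this "would have 82% power when the incidence of HSFR in the intervention arm is 30" percent.

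Section 13.1 makes all-grade reaction a parallel secondary endpoint. Nowhere is there an all-grade power that allows for the look, or a statement that the 82% leaves it out.

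**The concern.** The 82% depends on having 35 patients per arm, and the design does not guarantee that. If the look fails, the all-grade comparison has 14 per arm. The chance of detecting 55% v 30%, judged before the trial starts, must therefore be below the fixed-sample figure.

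The order of the two power statements points the same way. Both use 35 per arm, the same test, the same level and a 25-point difference. The all-grade pair has the larger binomial variance, so on a common basis its power must be the lower of the two. The plan shows the reverse, 82% against 80%. A reader would conclude that the secondary comparison is the better powered, and would take the planned risk of missing the all-grade effect to be 18%.

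**Working it through.** **Inputs (section 13.2).** All-grade 55% v 30%; grade-2-or-higher 50% v 25%, with control 40-50%; 35 per arm at the end, 14 per arm at the look; one-sided 0.10 (critical value 1.2816); stop if Z > -0.107.

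**1. Reproduce the 82%.** With d = 0.55 - 0.30 = 0.25:
- Unpooled SE = sqrt[(0.55×0.45 + 0.30×0.70)/35] = sqrt(0.4575/35) = 0.1143.
- Pooled SE = sqrt[2×0.425×0.575/35] = 0.1182.
- Unpooled power: Φ(0.25/0.1143 - 1.2816) = Φ(0.905) = 81.7%.
- Pooled power: Φ[(0.25 - 1.2816×0.1182)/0.1143] = Φ(0.862) = 80.6%.
- Exact binomial enumeration of the chi-squared test: 79.5%.

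The 82% is therefore a fixed-sample figure from a normal approximation.

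**2. Put the primary endpoint on the same footing.** Fixed-sample power for 50% v 25% is 81.8% pooled and 83.0% unpooled, above the all-grade figures as expected. The plan states 80%. A binding futility boundary with the final critical value lowered to 1.208, which restores the 0.10 level, gives 80.4%. The primary figure thus fits a calculation that includes the look.

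**3. Chance of stopping at 28 (50% v 25%).** SE at the look = sqrt[(0.25 + 0.1875)/14] = 0.1768. P(stop) = 1 - Φ(0.25/0.1768 - 0.107) = 1 - Φ(1.307) = 9.6%. Exact enumeration gives 11.3%.

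**4. Overall all-grade power.** This is the probability of passing the look on grade 2 or higher and then having all-grade Z ≤ -1.2816 at 35 per arm. Grade 2 or higher is nested in all-grade, so with grade-2-or-higher rate g and all-grade rate a, the covariance in an arm is g(1 - a):
- Summed over arms: 0.50×0.45 + 0.25×0.70 = 0.400.
- Patient-level correlation: 0.400/sqrt(0.4375×0.4575) = 0.894.
- Correlation between interim and final Z: 0.894×sqrt(14/35) = 0.565.
- Unpooled: Φ₂(1.307, 0.905; 0.565) = 77.4%. Pooled: Φ₂(1.303, 0.862; 0.565) = 76.4%.

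The same steps for other control rates, and a simulation of binomial counts (1,000,000 trials), give:

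| Grade ≥2, control v tazarotene | Stop at 28 (exact) | Unpooled normal | Pooled normal | Simulation |
|---|---|---|---|---|
| No look | – | 81.7% | 80.6% | 79.5% |
| 50% v 25% | 11.3% | 77.4% | 76.4% | 74.6% |
| 45% v 25% | 17.5% | 73.6% | 72.7% | 70.5% |
| 40% v 25% | 25.5% | 68.1% | 67.3% | 64.7% |

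**5. Separate the look from the method.** Down each column, the look costs 4.3, 4.2 and 4.9 points at 50% v 25%, and about 13 to 15 points at 40% v 25%. The 2.2 points between 81.7% and 79.5% are approximation, not the look.

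**6. Sensitivity.** Testing the 14-per-arm data after a stop changes little: 74.6% at 50% v 25% and 66.7% at 40% v 25%. A larger grade-2-or-higher effect raises the overall power: by simulation, 77.0% at 50% v 20% and 78.4% at 50% v 15%.

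**7. Power given that 35 per arm is reached.** By simulation at 50% v 25%: 74.6%/(1 - 0.113) = 84.1%. At 45% v 25% it is about 85%, and at 40% v 25% about 87%.

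**The case against.** The strongest reply is that the sentence carries its own condition, 35 per arm, and is right on that condition. It never claims to be the overall power of a two-stage design. The futility rule and the 28-patient minimum are stated openly in the same section, and quoting fixed-sample power at maximum size for a secondary endpoint is common.

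Much of this stands. A reader might infer an arithmetic error; there is none, since the figure reproduces. A reader might also infer that power is at most 75%. The calculations do not support that: both normal methods exceed 75% at the design rates, and a larger grade-2-or-higher effect gives more. Setting 82% against 74.6% and charging all 7 points to the look would mix two methods.

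A third tempting inference is that a null all-grade result would be badly over-read. That is weak. After a stop the reader sees 14 per arm, and in a trial that reaches 35 per arm the power in these scenarios is above 82%. The overall figure matters for planning.

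Finally, the 65-68% rests on a joint scenario that the plan does not state: a 40% control rate, 25% on tazarotene and an unchanged all-grade effect. At 40% v 15%, simulation gives 74.7%.

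What does not stand is that the 35-per-arm clause discloses the omission. The primary 80% carries the same clause and appears to allow for the look, so the clause does not tell the reader which basis applies.

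**Conclusion.** The concern holds as a matter of labelling and consistency. The 82% is fixed-sample power; the primary 80% beside it appears to include the futility look. That last point is inferred from the fit in step 2, because the plan does not give the final critical value.

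Overall all-grade power with the look is about 75-77% at 50% v 25% and about 65-68% at 40% v 25%. The second range corresponds to missing the targeted effect about one time in three.

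Assumptions: the look uses the primary endpoint and the rule is followed; enrolment stops at exactly 14 per arm; the all-grade test keeps the critical value 1.2816; grade 2 or higher is nested in all-grade with no further dependence; and the all-grade rates stay at 55% v 30%.

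Importance is modest, since this is a secondary endpoint in a signal-detection trial and the primary comparison sets the size.

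**What to change.** In section 13.2:

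- Label the 82% (about 80% by exact calculation) as fixed-sample power at 35 per arm with no interim look.
- Add that overall all-grade power including the futility look is about 75-77% under the 50% v 25% design scenario, and may fall to about 65-68% if the control grade-2-or-higher rate is 40% with 25% on tazarotene and the all-grade effect unchanged. State the assumptions.
- Say whether the primary 80% includes the look, and with which final critical value.

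The 80% should not be described as power conditional on reaching 35 per arm. Trials that reach it have passed a favourable look on a nested endpoint, and their power in the scenarios above is about 84-87%.

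The cost is two or three sentences and a less favourable figure. Sample size, test and stopping rule are unchanged.
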